## Measures

**Demographic variables.** Self-reported data will be collected on gender, age, level of education, length and degree of sick leave, length of mental health problems and marital status. Primary and secondary F-diagnosis (ICD-10) will be reported by the eTherapist.

**Questionnaires.** *Primary outcome measures:* The reduction in the degree of sick leave is one of our primary outcomes and will be measured through self-report. The first question is: “are you currently on sick-leave?”. The second question is activated if there is a positive answer to the first: ” To what degree are you currently on sick-leave?”. The answer is given on a 0-100 scale with 5 point increments.

The Return to Work Self-Efficacy Scale (RTWSE-11; (Lagerveld et al. 2010, Gjengedal et al. 2021) is an 11-item questionnaire measuring an individual’s confidence in their ability to work and perform work tasks. Items are scored on a scale from 1 (“Totally disagree”) to 6 (“Totally agree”). Items 2 and 6 are reversed. Total scores of 3.7 or below are associated with less probability of returning to work, while scores of 4.6 and above are associated with increased probability of returning to work (Gjengedal et al. 2021).

*Secondary outcome measures:* The Generalized Anxiety Disorder-7 (GAD-7; (Spitzer et al. 2006) is a measure of worry and anxiety and consists of seven items scored from 0 (“Not at all”) to 3 (“Nearly every day”) and one additional item measuring how the symptoms affect functioning. The Patient Health Questionnaire-9 (PHQ-9; (Kroenke, Spitzer & Williams 2001) measures depression severity. The measure consists of nine items scored from 0 (“Not at all”) to 3 (“Nearly every day”). The Work and Social Adjustment Scale (WSAS; (Mundt et al. 2002) measures impairment in functioning. The measure consists of five items scored from 0 (not at all impaired) to 8 (very severely impaired). CORE-OM (Evans et al. 2002) is a 34-item self-report, measuring well-being, symptoms, elements of risk, and function on a five-point scale ranging from “not at all” to “most, or all the time”. CORE-10 (Barkham et al. 2013) is a ten item self-report measuring symptoms, well-being, functioning and risk on a five-point scale ranging from “not at all” to “most, or all the time”. The Negative Effects Questionnaire (NEQ) (Rozental et al. 2016, Rozental et al. 2019) is a 20-item questionnaire evaluating adverse or unwanted events during treatment. Participants report whether a specific event occurred during treatment (“Yes”/”No”) and then indicate how negatively they were affected by it on a scale ranging from 0-4. An adapted version of the Credibility Rating Scale (Borkovec & Nau 1972) will be used to assess treatment credibility. The scale consists of five items where participants rate their credibility/expectancy-for-improvement on a 10-point scale.

**System data on user behaviour.** Data on use and user behaviour will be extracted from the system and combined with data from the self-report questionnaires collected. Information about the actual program use will be generated by the e-health platform Youwell. The data includes the extent to which participants complete the treatment, where and when they drop out, and how long they need to complete individual parts. Further we will look into whether there are areas in the treatment that require more time than others, which elements are used

most and least frequently, and how the therapist guidance is used. Further we also will analyse how long each session lasts and what system and platform they use. Each eBehandling location will also maintain local statistics on the number of assessment interviews, participants included and excluded to assess acceptance in the patient population and hospital setting. This data collection will be recorded by on-site super users. Efforts will be taken to ensure that this registration is implemented in the Youwell platform.

**Qualitative in-depth interviews.** Two months after completion of the program, a subset of participants will be invited to an in-depth interview (See Appendix A for the complete Interview Guide). We will use purposive sampling to select participants who represent a diverse range of demographics (age, gender) and outcomes (treatment responders and non-responders). Care will be taken to include participants from different treatment sites. We aim to recruit a total of 20 participants for the qualitative interviews, likely ensuring richly-textured information on a broad array of participant experiences.

The interview has a semi-structured design with six questions and related probes (See Appendix A for the complete Interview Guide). The interviews will be conducted by research fellow [name]. The interviews will focus on the participants' experience of the feasibility of the intervention, including aspects of the treatment viewed as helpful and less helpful. All interviews will be audio recorded and transcribed verbatim.

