### **Study aims**

The main aim of the current study is to investigate the utility and use of a digital transdiagnostic work-focused CBT treatment program for patients with common mental health disorders on sick leave or work assessment allowance. This includes the user experience of participation and experienced utility of the treatment program. Secondary aims are related to mediators and moderators of treatment efficacy and the participants' experience with the program.

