## **Hypotheses of main effects**

**H1a.** We expect a large main effect of treatment on total percentage sick leave from pre- to post treatment, with gains maintained at follow up.

**H1b.** We expect a large main effect of treatment on the number of participants with full return to work from pre- to post treatment, with gains maintained at follow up.

**H2.** We expect a large main effect of treatment on reduction on symptoms of depression and anxiety.

**H3.** We expect a positive main effect of treatment on Return to Work Self-Efficacy, from pre to post treatment, and sustained through follow up.

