## **Hypotheses of moderating and mediating effects and predictors of outcome**

**H4.** We expect a negative relationship between duration of baseline work absenteeism and degree of return to work at post. Baseline work absenteeism will moderate the relationship between treatment and return to work.

**H5a.** We expect treatment credibility at baseline to be predictive of treatment adherence.

**H5b.** We expect that treatment adherence will be a mediator between treatment credibility and treatment outcome.

**H6.** We expect changes on the Return to Work Self-Efficacy Scale to predict the degree of absenteeism post treatment.

**H7.** We expect change on the Return to Work Self-Efficacy Scale to be a mediator between baseline absenteeism and return to work post-treatment.

**H8.** We expect higher depression scores (PHQ-9/CORE-OM score) to be a moderator between treatment credibility and treatment outcome and adherence.

**H9.** We expect that fewer than 10% of participants experience negative effects caused by participation, as measured by the Negative Effects Questionnaire (NEQ).

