## Methods and procedures

### Design

This study is a non-randomized, single arm, multi-center mixed methods clinical trial in a naturalistic setting (see Figure 1 for an overview of the study design). Participants are recruited in a real life setting in Norwegian specialised mental health care. After recruitment participants fill out questionnaires pre, interim and post treatment, in addition to follow up at 6 and 12 months after completing treatment. Interim measures are collected after six weeks. After the treatment intervention, some participants are invited to an in-depth qualitative interview.

[figure not shown]

Figure 1. Study design.

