## Sample

Inclusion criteria for the sample are 1) being an outpatient in specialised mental health care service, 2) above 18 years old, 3) full or graded sick leave, or on work assessment allowance 4) primary diagnosis of F30 – F40 (ICD-10), 5) currently employed.

Exclusion criteria are 1) ongoing psychotic disorder and/or mania, 2) ongoing substance abuse, incl. sedative medications, 3) ongoing episode of major depression, 4) organic brain disease, 5) severe reading and writing difficulties.

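### The primary work item asks only about sick leave although people on work assessment allowance are eligible, so their absence can go unrecorded and a later no is ambiguous

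*Protocol*

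**What the plan says.** Inclusion criterion 3 (Protocol, Sample) accepts "full or graded sick leave, or on work assessment allowance", and criterion 5 requires the participant to be "currently employed". The Study aims name the same two groups: "patients with common mental health disorders on sick leave or work assessment allowance". Both places present the allowance as an alternative to sick leave, so a person can qualify on the allowance alone.

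Under Measures, the work outcome is one of two primary outcomes and consists of two self-report questions. The first asks whether the respondent is on sick leave now. The second asks for the degree, from 0 to 100 in steps of 5, and is conditional: "The second question is activated if there is a positive answer to the first". The demographic item on absence is also worded as sick leave.

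H1a concerns "total percentage sick leave from pre- to post treatment, with gains maintained at follow up". H1b states: "We expect a large main effect of treatment on the number of participants with full return to work from pre- to post treatment". H6 expects change in self-efficacy "to predict the degree of absenteeism post treatment". Questionnaires are given before, during and after treatment, "in addition to follow up at 6 and 12 months after completing treatment". Statistical analyses lists sick leave as a dependent variable of the mixed models.

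**The concern.** The population is defined by two benefit statuses and the outcome asks about one of them. No other measure described in the protocol records allowance status, hours or actual work. RTWSE-11 measures confidence and WSAS measures impairment.

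At baseline, a recipient who answers no never sees the degree question, so that person's starting level of absence is not recorded. At later visits, a no comes both from someone fully back at work and from a recipient still off work, and the two records are identical. H1a and H1b have no other described source. H4, H6 and H7 speak of return to work or absenteeism without naming an item, and no other item is described that could supply them. With a single arm, no control group shares the misclassification, so it passes straight into the before-after change.

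**Working it through.** **What a no can mean**

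| Visit | Participant | First question, answered literally | Degree recorded |
|---|---|---|---|
| Baseline | On sick leave | yes | yes |
| Baseline | On the allowance | no | none |
| Later | Fully back at work | no | none |
| Later | On the allowance, still off work | no | none |

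At baseline, criterion 3 resolves the no: eligibility requires one of the two statuses and is assessed for each participant (Procedure), so a no points to an allowance recipient. Nothing comparable separates the last two rows. Criterion 5 does not help, because everyone on full sick leave also meets it: being employed is not the same as being at work.

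**Size**

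The protocol gives no allowance share or return rate, so there is no figure of its own to reproduce. The inputs below are assumptions, except the 300 participants from Power analyses:

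- r = share truly returned = 0.30;
- b = share of the sample who are recipients and answer no = 0.10 to 0.30;
- recipients return at the same rate as others, and nobody changes benefit;
- true absence is 80% at baseline, stays at 80% in those not returned and is 0% in those returned.

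*H1b, rule A: baseline return fixed at zero by criterion 3, a later no counts as return.*
Recorded rise = r + (1 - r)b, so the overstatement is (1 - r)b.
- b = 0.10: 0.7 × 0.10 = 7 points, or 21 of 300
- b = 0.20: 0.7 × 0.20 = 14 points, or 42 of 300
- b = 0.30: 0.7 × 0.30 = 21 points, or 63 of 300

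*H1b, rule B: a no counts as return at both visits.*
Recorded rise = [r + (1 - r)b] - b = r(1 - b), against a true rise of 30 points.
- b = 0.10: 0.30 × 0.90 = 27 points, understated by 3
- b = 0.20: 0.30 × 0.80 = 24 points, understated by 6
- b = 0.30: 0.30 × 0.70 = 21 points, understated by 9

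*H1a, a no scored as 0% at both visits.*
True fall = 80 × 0.30 = 24 points. Recorded fall = 80(1 - b) - 80(1 - r)(1 - b) = 80r(1 - b).
- b = 0.10: 21.6
- b = 0.20: 19.2
- b = 0.30: 16.8

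*H1a, baseline degree left missing but a later no scored as 0%.*
The crude difference in means is 80 - 80(1 - r)(1 - b).
- b = 0.10: 80 - 50.4 = 29.6
- b = 0.30: 80 - 39.2 = 40.8

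The true fall is again 24, so the sign reverses. A mixed model would not return exactly this difference, but the later zeros would pull it the same way.

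*If every recipient answers yes*, b = 0 and the error is zero under all four rules.

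**The case against.** Several points on the other side stand.

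- **Direction.** A reader might infer that H1b can only be overstated. The documents do not support that. The protocol does not say that a no counts as full return, nor how a baseline no is scored, and rule B gives an understatement. The 7-21 points belong to rule A alone.
- **What an analysis plan could do.** A reader might infer that no scoring rule can help at all. That is too strong. A baseline no can be flagged as an allowance recipient, and that person's later no can be treated as indeterminate. What scoring cannot recover is narrower: the flagged person's true later status, and any later change of benefit.
- **Moves between benefits.** A reader might infer that participants often pass from sick leave to the allowance and so appear recovered. No passage says that this happens, when, or how often, so no figure for it is given here.
- **How recipients read the question.** The protocol itself uses sick leave for the whole sample, for instance in the title of Paper I, so some recipients may answer yes. That can shrink the error to zero. It can also make answers inconsistent between people with the same status.
- **What is not shown.** Figure 1 and the deployed forms are not available, so an extra item cannot be ruled out. The Measures section describes none.
- **Limited reach.** Criterion 5 restricts which recipients can enter, the study seeks preliminary results, and RTWSE-11 and the symptom scales do not depend on this item.

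None of this closes the gap itself: an eligible group has a status that the primary work item does not ask about.

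**Conclusion.** The point holds as a fault in data collection that should be fixed. As described, the item can leave an allowance recipient without a baseline degree of absence, and it cannot tell that person's continued absence from full return later.

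The direction is not fixed. With 30% truly returned and 10-30% of the sample being recipients who answer no, H1b is off by +7 to +21 points or by -3 to -9 points, depending on the scoring rule. A true 24-point fall in H1a reads as 21.6-16.8 if a no is scored as 0% throughout, and as larger than 24 if only the later no is. These figures show what is possible; they are not estimates. They rest on assumed shares, on equal return in both groups and on literal answering.

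**What to change.** Keep both existing items unchanged, so that the series stays comparable. Add at each remaining visit one question put to everyone, outside the sick-leave branch: whether the participant currently receives work assessment allowance, and to what extent they are working. Then state that:

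- a participant still on the allowance and off work does not count as full return in H1b;
- a baseline no is not scored as 0% absence in H1a, and a later no from the same participant is scored as 0% only if the added question confirms it;
- H1a and H1b are also reported by baseline benefit type, as a sensitivity analysis.

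There is no need to redefine full return in terms of contracted hours; that would go further than the fault requires.

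The cost is one extra item in the platform, one scoring statement and one sensitivity analysis. Visits already completed lack the item and must be reported on the original questions. For those participants, baseline benefit type can be inferred only from a baseline no, so recipients who answered yes stay unidentified. Site eligibility records might fill that gap but may not be linkable, since the research export gives no access to personal profiles (Data and privacy protection).

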### **Research questions**

1. To what extent does the treatment program impact Return to Work, self-reported symptoms, and everyday functioning?
2. To what extent do clinical, work-related and demographic factors affect treatment adherence and treatment response?
3. To what extent do adherence and changes in work-related self-efficacy predict outcomes?
4. What type and frequency of negative effects does participants report?
5. How do participants describe their experience of use and utility of the program, as well as its challenges and benefits?

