## Power analyses

In a multilevel model, the fixed effects are comparable to ordinary repeated t-tests, and thus, using this as a proxy model with a moderate effect size ( $d = 0.6$ ), power = 0.8, alpha = 0.05, tails = "two.sided", we need 25 subjects for detecting a single main effect Murayama, Usami and Sakaki (2022); see [Summary-statistics-based power analysis \(shinyapps.io\)](#). But, as stated by Van Voorhis and Morgan (2007): "*if the circumstances allow, a researcher would have better power to detect a small effect size with approximately 30 participants per variable*" (page 48). Following this rule of thumb, we plan for 30 participants per predictor (unique main effects), thus a total sample size of 300 participants. Calculating a drop-out rate of 30% gives a total sample size of  $N = 390$ . Calculating power for indirect effects – or mediation – we used the following online shiny app [Monte Carlo Power Analysis for Indirect Effects \(shinyapps.io\)](#), published by Schoemann, Boulton and Short (2023). Using (El Alaoui et al. 2015) as a proxy study for the direction and strength of association between our variables, they found that both treatment credibility and treatment adherence were significantly predictors of faster change and lower post treatment scores in a routine psychiatric care based ICBT for social anxiety disorder. In the same study, a high level of treatment credibility was associated with higher treatment adherence. Hence, defining X = treatment credibility, M = treatment adherence and Y = treatment outcomes, we set the correlation of X-M (a-path) = 0.3 ( $SD = 1$ ), X-Y (c-path) = 0.30 ( $SD = 1$ ) and M-Y (b-path) = 0.30 ( $SD = 1$ ), power = 0.8, alpha = 0.05, setting random seed to "0512", using 5000 replications with 20000 Monte Carlo draws per replication, we need  $N = 155$  to have a power of 0.80, 95% CI [0.79-0.82].

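### The interview sampling rule is tied to completing the programme and does not use completion status, so nothing ensures that participants who stop early are among the 20 interviewed

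*Protocol*

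**What the plan says.** The qualitative paragraph under Measures is the only place in the Protocol that fixes both when interviewees are approached and how they are chosen. On timing it says: "Two months after completion of the program, a subset of participants will be invited to an in-depth interview". On selection it asks for a "diverse range of demographics (age, gender) and outcomes (treatment responders and non-responders", and adds: "Care will be taken to include participants from different treatment sites". The number is also fixed: "We aim to recruit a total of 20 participants for the qualitative interviews". Whether a person completed the programme or stopped early is not among the criteria.

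Two other sections mention the interviews more briefly. Design says: "After the treatment intervention, some participants are invited to an in-depth qualitative interview". Procedure says that participants will be asked to take part in a voluntary interview, with no trigger and no categories.

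The interviews serve research question 5: "How do participants describe their experience of use and utility of the program, as well as its challenges and benefits". The qualitative analysis section adds that patient accounts may help to find difficulties with the treatment protocol and improve later delivery. The third planned paper rests on these interviews.

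For participants who drop out, Procedure and the ethics section on drop-out describe local clinical follow-up and other treatment. Neither mentions an interview.

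**The concern.** People who leave a programme early are an obvious source on what made it hard to use. If the invitation depends on finishing, and finishing is not a sampling criterion, the account of utility and challenges may come entirely from people who stayed. That would tilt the answer to research question 5 towards acceptability and could leave out the reasons for stopping.

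This bears on the main aim, because Study aims counts user experience and experienced utility as part of it (participants' experience is also listed among the secondary aims). It cannot be repaired at the analysis stage: once the 20 interviews are used, the missing accounts are gone. Nor is it a matter usually left to a statistical analysis plan, since the Protocol itself sets the sampling rule.

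**Working it through.** This is mainly a check of the text, with simple arithmetic for scale.

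**Step 1. Does the invitation rule reach an early stopper?** The trigger is completion of the programme plus two months. The subsection on system data treats completing the treatment and dropping out as contrasting events. On that usage a participant who stops early has no completion date, so the two-month clock never starts. Design and Procedure are worded more broadly, but neither supplies an alternative trigger.

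**Step 2. Do the sampling criteria bring early stoppers in?** The criteria are age, gender, response and site. The nearest to completion status is "outcomes (treatment responders and non-responders". A participant who finishes all seven modules without improving is a non-responder. The non-responder places can therefore be filled by completers alone, and every stated criterion can be met with no early stopper among the 20.

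**Step 3. Does another data source give the same information?** The system data record how far participants get and where and when they drop out. They do not record the participant's reasons. The contact made after seven days without login is part of clinical follow-up and is not described as a source of qualitative data.

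**Step 4. Scale.** Inputs from the Protocol are 300 participants before allowance, 30% drop-out, N = 390 (Power analyses) and 20 interviews (Measures).

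- The plan's own figure: 300 × (1 + 0.30) = 390. This reproduces the stated total. Whether that is the right way to allow for drop-out is a separate matter and does not affect this point.
- If the 30% meant leaving the programme: 0.30 × 390 = 117 early stoppers, and 0.30 × 20 = 6 interviews as a proportionate share.
- The section says only "Calculating a drop-out rate of 30% gives a total sample size of" 390, without stating whether drop-out means leaving the programme or missing measurements. Programme drop-out is therefore not given. Over an assumed range:

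| Assumed programme drop-out | Proportionate share of 20 interviews |
|---|---|
| 10% | 0.10 × 20 = 2 |
| 20% | 0.20 × 20 = 4 |
| 30% | 0.30 × 20 = 6 |
| 40% | 0.40 × 20 = 8 |

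The rule as written guarantees 0 at every row.

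**The case against.** The strongest reply is that the Protocol nowhere restricts interviews to completers. Design refers to some participants after the intervention, and Procedure to participants in general. Completion may simply mark the end of the 12-week course: Design times the 6- and 12-month follow-ups from completing treatment, and Procedure counts six months of further access from completion. Non-responders are expressly sought, and no passage says that early stoppers are not asked for post-treatment measures. Interim data at six weeks and the weekly CORE-10 might also allow them to be classed. Much of this stands. A reader might infer that drop-outs are excluded or cannot be heard, and the text does not support that.

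A reader might also take 117 participants as having no chance of selection. That does not follow either, because it treats an undefined sample-size allowance as programme drop-out.

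One might go further and calculate the chance that a given barrier is mentioned at all. Such a figure would rest on assumed rates in completers and stoppers. It would also count mentions, which reflexive thematic analysis of a purposive sample does not do. It is not relied on here.

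The reply does not remove the gap. Even if completion means the end of 12 weeks, completion status is still not a criterion and Step 2 still holds. The interview guide (Appendix A) is not among the material at hand, so nothing is claimed about its content.

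**Conclusion.** The point holds in a limited form. The Protocol does not define completion for the purpose of the invitation and does not name early stopping as a sampling category. Read literally, the rule misses participants who stop early; on the more generous reading, they may be invited but nothing ensures it. This is a weakness in design, not a demonstrated exclusion or a contradiction.

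The likely consequence is an account of utility and challenges weighted towards those who stayed. The size is indicative: 2 to 8 of 20 interviews on a proportionate basis, assuming 10% to 40% programme drop-out, and 6 if the planned 30% is taken as programme drop-out. No sample-size figure and no quantitative analysis is affected. It is worth changing because the change is cheap and the loss cannot be recovered later.

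**What to change.** In the qualitative paragraph under Measures:

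1. Time the invitation at two months after completing or stopping the programme. Alternatively, time it from the end of the 12-week period for everyone. Either way, state what completion means.
2. Add completion status (completed or stopped early) to the purposive criteria, so that some of the 20 interviews are with early stoppers. A fixed quota is not needed, since programme drop-out is unknown and 20 interviews must also cover age, gender, response and site.
3. Align the one-sentence descriptions in Design and Procedure with this rule.
4. Check that the interview guide covers reasons for stopping, and add a probe if it does not.

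The invitation would go only to early stoppers whose research consent still stands.

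The cost is a few lines of text. The total of 20 and the interviewer stay the same, and no treatment procedure changes. The downside is that early stoppers are harder to recruit and slightly fewer completers will be interviewed.
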